8.9 Proportion of patients receiving prolonged treatment

The proportion of patients receiving prolonged treatment is based on a binary variable which indicate whether a patient has received prolonged treatment or not, i.e. received study treatment on at least one of the days 7, 9, 11, or 13.

8.10 Proportion of patients receiving rescue treatment on Day 14

The proportion of patients receiving rescue treatment (an antibiotic treatment, as defined in the CIP) on Day 14 is based on a binary variable which indicate whether a patient has used rescue treatment or not, i.e. as shown by collected CRF concomitant medication data, where start date of the rescue medication should be from or after Day 14. Start and stop date of use of such rescue medication will be presented in data listings.

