Name of Sponsor: Gedea Biotech AB
Name of Products: Gedea Pessary (commercial name pHyp)
Name of Active Ingredient: Glucono-delta-lactone (GDL) and sodium gluconate (NaG)
Title of Study: An open-label study to evaluate clinical performance of Gedea Pessary in adult women with bacterial vaginosis (BV).
Clinical Investigation Plan Number: QRS-CL2-003
Investigators and Study Center(s): NAME , VO Kvinnosjukvård, Skånes universitetssjukvård, Lund, Sweden NAME , Stortorgets Gynekologmottagning, Helsingborg, Sweden NAME , MD, Capio Novakliniken Sjöstad, Ystad, Sweden Kliniska prövningssenheten, Kliniska Studier Sverige - Forum Söder, Skånes universitetssjukhus, Lund, Sweden
Classification of Trial: Feasibility Clinical Investigation
Objectives: To investigate the clinical performance, tolerability, and safety of the investigational product.
Methodology: This is an open-label, single-armed, multi-center study to evaluate clinical performance, tolerability, and safety of Gedea Pessary in 24 adult women with confirmed BV according to fulfillment of at least 3 of the 4 Amsel criteria. On Day 0, patients will have gynecological examination, vaginal samples taken, and will receive 4 doses of the investigational product to be self-administered 2 days apart (Day[s] 0, 2, 4, and 6). Patients will be examined after 7 days with respect to 3 Amsel criteria (the criterion: "pH of vaginal fluid above 4.5" is only included at study inclusion for diagnosis), and if not cured, will receive prolonged treatment to be administered on Day(s) 7, 9, 11, and 13. Patients will be followed-up by telephone up to 29 days after last treatment. Vaginal samples will be used for confirming diagnosis and microbiome analyzes. Patient questionnaires will be used for assessing BV symptoms, usability, and adverse events (AEs).
Number of Subjects Planned: Twenty-four (24) patients

Diagnosis and Main Criteria for Inclusion:

Inclusion Criteria:

- Adult, post-menarchal, pre-menopausal women aged 18 years or older
- Diagnosis of BV according to Amsel's criteria, defined as having at least 3 of the 4 following criteria:
 1. Thin, white, yellow, homogenous discharge
 2. Clue cells on microscopy (more than 20 percent of epithelial cells)
 3. pH of vaginal fluid above 4.5
 4. Release of fishy odor "i.e. a positive whiff test" when alkali (10% potassium hydroxide [KOH] solution) is added
- Having decisional capacity and providing written informed consent
- Negative urine pregnancy test at screening

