3.5.4 Day 6; Treatment Administration

Procedures performed:

- Treatment self-administration by patients

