3.5.5 Day 7 (+2 Days); Follow-up Visit

Patients will visit the clinic on Day 7 to have gynecological examination performed where the Investigator or an authorized designee will assess the presence of BV according to 3 Amsel criteria. Vaginal samples will be collected by swab to be used for vaginal microbiome sequencing analysis and vaginal pH assessed for product *in vivo* duration.

If BV symptoms are still present according to Amsel's criteria, patients will have prolonged treatment and receive additional doses of investigational product to be administered at home on Day(s) 7, 9, 11, and 13.

In addition, patients will be asked questions from the patient questionnaire to assess: symptoms of BV (fishy smell, irritation, and burning); usability; concomitant medications; and AEs, if any.

Procedures performed:

- Gynecological examination by Investigator or an authorized designee assessing the presence of BV according to the following Amsel criteria:
 - Presence of thin, white, homogenous discharge
 - Presence of clue cells on microscopy (more than 20% of epithelial cells)
 - Release of fishy odor "i.e. a positive whiff test" when alkali (10% potassium hydroxide [KOH] solution) is added
- Symptoms of BV (fishy smell, irritation, and burning) evaluated by patients according to a scoring scale (0-3)
- Vaginal swab for sequencing
- Vaginal pH
- Recording of:
 - concomitant medications,

- adverse events, and
- usability
- Treatment dispensing and self-administration by patients if receiving prolonged treatment

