3.5.7 Day 11 (+2 Days); Follow-up Telephone Contact

Applicable to patients receiving prolonged treatment

Patients receiving prolonged treatment on Day 7 will self-administer the investigational product and will be contacted by the Clinical Trial Unit by telephone on Day 11. Telephone contact up to Day 13 will be allowed if Day 11 falls on a weekend. The treatment should nevertheless be self-administered on Day 11. Patients will be asked questions from the patient questionnaire about: BV symptoms of fishy smell, irritation, and burning; concomitant medications; and AEs, if any.

Procedures performed:

- Treatment self-administration by patients
- Symptoms of BV (fishy smell, irritation, and burning) evaluated by patients according to a scoring scale (0-3)
- Recording of:
 - concomitant medications, and
 - adverse events

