Unless stated otherwise, the baseline value for a parameter is defined as the last non-missing value before the first self-administration of the study treatment by the patient. The first self-administration is to be performed on the same day as the first study visit (Day 0), after the study visit.

7.1.3 *Analysis relative day*

The analysis relative day for an assessment/value is defined as the time in days from the date of first administration of treatment to the date of the assessment. The date of first administration of treatment is considered as day 0.

7.1.4 *Analysis visit*

An analysis visit is defined as a categorical variable used to classify values within an analysis variable into temporal or conceptual groups used for analyses.

The visits as defined in the case report form, CRF, will be used as analysis visits.

In general, data from unscheduled visits will be presented in data listings only and not included in analysis or summary tables. An exception to this is data used to confirm eligibility in association with screening or randomisation where the last assessment will be considered in summaries of screening data.

7.1.5 *Handling of missing data*

The statistical analysis will be based on the observed data, i.e. no imputation is planned. In case of one or more missing symptom value(s) in the 3 BV symptoms, the sum of the 3 BV symptoms scores will be set to missing, see also [Section 8.7](#) below.

7.1.6 *Interim analyses*

Not applicable.

7.1.7 *Multiplicity*

Although there are two co-primary endpoints, no adjustment of e.g. p-values or confidence intervals will be applied. This is for two reasons, the first being that the evaluation of the second co-primary endpoint (safety and tolerability) will only be based on descriptive statistics and data listings, and the second is that both co-primary endpoints have to show favorable results.

For all other statistical analyses of the secondary endpoints, no adjustment due to multiple testing will be performed. It should be noted that the probability of making a type I error increases with the number of statistical tests performed.

7.1.8 *Subgroups*

Descriptive results of the primary clinical performance endpoint will be presented by study center, and by whether the patients at Day 0 reported 3 or more Bacterial Vaginosis infections during the last 12 months or not.

7.2 *Analysis sets*

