The decision on the classification of patients to each analysis set will be taken at the clean file meeting and documented in the clean file report together with the reasons for excluding patients from analysis sets.

7.2.1 *Full analysis set*

Full Analysis Set (FAS): This is the primary population and comprises all patients entering the study and having received at least 1 dose of study treatment. Analyses of clinical performance will be performed against this population.

In addition to this, two sub-populations based on this FAS will be formed: “FAS (For patients not receiving prolonged treatment)”, and “FAS (For patients receiving prolonged treatment)”.

7.2.2 *Per-protocol analysis set*

Per Protocol (PP) Population - This will include all FAS patients without any major protocol deviation, i.e. patients who have completed the study and sufficiently complied with the study protocol, have available primary endpoint data and have received the study treatment according to protocol. The final definition of a major protocol deviation will be decided and defined at the clean file meeting and

documented in the clean file report. If a relevant number of patients are excluded from the PP population, then the analysis of the clinical performance endpoint will be provided for the PP population.

7.2.3 *Safety analysis set*

The safety analysis set will be based on the same definition as used for FAS. All safety analyses will therefore be performed against the FAS. All patients included in the FAS will be accounted for, including those who did not complete the study along with the reasons for withdrawal.

7.3 *Disposition of patients*

The following will be presented:

- Number of screened patients, in total.
- Number of screening failures, in total.
- Number of enrolled patients.

Based on the number of enrolled patients, the following will also be presented:

- Number and percentage of patients who did not receive any dose of study treatment.
- Number and percentage of patients who received at least one dose of study treatment.
- Number and percentage of patients who completed the study.
- Number and percentage of patients who withdrew prematurely from the study.
- Number and percentage of patients in each of the analysis sets.

In addition, a frequency table on the primary reason for premature withdrawal from the study will be presented. Percentages for this table will be based on the number of prematurely withdrawn patients.

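### SAP 8.9 flags prolonged treatment by listed dosing days, not by dispensing: a late fourth dose counts as prolonged, and a second course moved wholly to even days does not

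*SAP*

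**What the plan says.** SAP 8.9 derives a yes/no variable for prolonged treatment. It is yes if the woman "received study treatment on at least one of the days 7, 9, 11, or 13". This is the only definition of prolonged treatment in the SAP text available.

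The Protocol forms the group differently. Under Protocol 3.1, prolonged treatment goes to women not cured at the Day 7 examination. That visit has a window, "3.5.5 Day 7 (+2 Days); Follow-up Visit", so it may fall on Day 7, 8 or 9. Women who are not cured then "receive additional doses of investigational product to be administered at home on Day(s) 7, 9, 11, and 13". Those days carry no window, and nothing is said about a visit that takes place on Day 8 or 9.

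For the first course, the Protocol synopsis has doses "self-administered 2 days apart (Day[s] 0, 2, 4, and 6", and the last of these has its own entry without a window, "3.5.4 Day 6; Treatment Administration".

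Prolonged status is used elsewhere in the SAP. In SAP 7.2.1, "two sub-populations based on this FAS will be formed", one for women with prolonged treatment and one for women without. SAP 7.8 sets the expected amount at 8 doses or 4 doses on the same distinction. Neither section cites 8.9.

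**The concern.** What makes a woman prolonged is a decision at a visit followed by a second pack. The SAP replaces this with a list of days on which any study dose counts. The two agree when every dose and visit is on schedule. They can part when a home dose is a day late, or when the visit uses its window and the second course moves with it.

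The proportion receiving prolonged treatment is itself a secondary endpoint. If the same variable also forms the sub-populations in SAP 7.2.1, it decides who is analysed for cure on Day 14 and for recurrence on Days 14 and 35 or Days 21 and 42. A woman in the wrong group would be assessed at visits she did not have and left out of those she did.

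The rule also needs a date for each dose. Protocol 5.8 and SAP 7.8 describe only questions about administration on Days 4 and 7 (and 11 and 14). Neither document says that individual dose dates are recorded.

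**Working it through.** **Inputs.** Planned number 24 and assumed cure rate 70% (Protocol 9.3, SAP 5.1). Listed days 7, 9, 11 and 13 (SAP 8.9). Visit window Day 7 to Day 9 (Protocol 3.5.5). Fourth dose on Day 6 (Protocol 3.5.4). Expected doses 4 or 8 (SAP 7.8). The plan gives no expected figure for the prolonged group, so there is none to reproduce.

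**Step 1: apply the rule literally.** A woman is flagged if any dosing day is 7, 9, 11 or 13.

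| Situation | Dosing days | Listed days hit | SAP 8.9 | By dispensing |
|---|---|---|---|---|
| Cured, on schedule | 0, 2, 4, 6 | none | no | no |
| Cured, fourth dose one day late | 0, 2, 4, 7 | 7 | **yes** | no |
| Not cured, visit Day 7 | 0, 2, 4, 6, then 7, 9, 11, 13 | all four | yes | yes |
| Not cured, visit Day 8, all doses moved | 0, 2, 4, 6, then 8, 10, 12, 14 | none | **no** | yes |
| Not cured, visit Day 8, starts that day, then planned days | 0, 2, 4, 6, then 8, 9, 11, 13 | 9, 11, 13 | yes | yes |
| Not cured, visit Day 8, remaining planned days only | 0, 2, 4, 6, then 9, 11, 13 | 9, 11, 13 | yes | yes |
| Not cured, visit Day 9, all doses moved | 0, 2, 4, 6, then 9, 11, 13, 15 | 9, 11, 13 | yes | yes |

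Two rows disagree. The first is a false yes and needs one late home dose. The second is a false no and needs both a Day 8 visit and a complete shift of the second course. The other five rows agree.

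**Step 2: effect on the endpoint.** At 70% cured, the expected prolonged group is 0.30 × 24 = 7.2 women. One error changes the count by one, so the proportion moves by 1/24 = 4.2 percentage points. Exact two-sided 95% intervals:

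- 6/24 = 25.0% (9.8% to 46.7%)
- 7/24 = 29.2% (12.6% to 51.1%)
- 8/24 = 33.3% (15.6% to 55.3%)

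One error is small against the width of these intervals.

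**Step 3: effect if the same flag is used in SAP 7.2.1 and 7.8.**

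- A cured woman with a late fourth dose has taken 4 of an expected 8 doses: 4/8 = 50% compliance.
- A missed prolonged woman with a full second course has taken 8 of an expected 4: 8/4 = 200%.
- The wrongly flagged woman has no Day 14 examination. SAP 7.1.1 keeps patients with missing data in percentage denominators unless stated otherwise. With 7 truly prolonged women and k cured on Day 14, the rate would become k/8 instead of k/7, that is, 7/8 of its value.

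**The case against.** The strongest reply is that the listed days are nominal labels for the second course. SAP 8.9 introduces them as an explanation of having received prolonged treatment, and SAP 7.1.4 takes its analysis visits from the case report form. The sentence that counts actual days, "The date of first administration of treatment is considered as day 0", is in SAP 7.1.3, which covers assessments and not doses. On the nominal reading neither error arises. That reading is possible, but it is not written. Table 3 of the Protocol gives Days 9 and 13 no visit number, so SAP 7.1.4 supplies no label for those doses.

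Second, the Protocol keeps dosing days fixed when a contact is late. For the Day 11 call it says "The treatment should nevertheless be self-administered on Day 11", and Day 4 is treated alike. If the same held after a late Day 7 visit, a woman seen on Day 8 would dose on Days 9, 11 and 13 and be flagged correctly. This stands as a limit on the second error, but those sentences concern telephone calls. The Protocol has no matching one for the Day 7 visit, and the second-course pessaries are dispensed at that visit.

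Third, the wider consequences are inferred. SAP 7.2.1 and 7.8 do not cite 8.9, the flow-chart text splits women by cure at Day 7, and analysis sets are settled at the clean file meeting, where a mismatch could be noticed. All of that is fair. The inference rests on 8.9 being the only definition given.

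Finally, the endpoint is a secondary proportion with a confidence interval and no hypothesis test. That limits the weight of the point, but does not make the rule correct.

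**Conclusion.** The point holds in a limited form. Read as calendar days, SAP 8.9 gives a wrong result in two identifiable situations: a cured woman whose fourth dose is taken on Day 7, and a woman seen on Day 8 whose entire second course moves to Days 8, 10, 12 and 14. Each such woman moves the endpoint by 4.2 percentage points. The effects on compliance and on the Day 14 cure denominator follow only if the same flag drives SAP 7.2.1 and 7.8. The primary endpoint, cure on Day 7, does not use the flag.

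A reader might infer that women seen on Day 8 are missed in general, and that an error is therefore likely. For example, suppose 1/7 to 1/3 of the Day 7 visits took place on Day 8. Then 7.2 × 1/7 = 1.0 to 7.2 × 1/3 = 2.4 women would be missed. Among 7 women the chance of at least one error would be 1 − (6/7)^7 = 66% to 1 − (2/3)^7 = 94%. The documents do not support this. They give no share of Day 8 visits, and the calculation also needs every woman seen on Day 8 to shift every dose, a schedule that the Protocol does not state. If none shift, the number missed is zero. A Day 9 visit causes no miss even when all doses shift. No frequency is given for late fourth doses either, so the frequency of both errors is unknown and may be zero.

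The SAP should still be changed, because the rule is wrong as written and the correction is cheap.

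**What to change.** In SAP 8.9, define a woman as having received prolonged treatment if a second pack was dispensed to her at the Day 7 (+2) visit and she took at least one pessary from it, on any calendar day. State that this flag forms the two sub-populations in SAP 7.2.1 and sets the expected amount in SAP 7.8. The table above shows that this corrects both discordant patterns and leaves the others unchanged.

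The cost is one definition and two cross-references, with no change to treatment or visits. The small downside is that dispensing or accountability data must be available for the analysis. Protocol 5.1.1 requires dispensing logs with the dispense date, units used and patient, and Table 3 schedules product accountability on Days 7 and 14. The logs are kept at the sites, however, and the Protocol does not say that they enter the study database. This should be confirmed before database lock.

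Separately, the Protocol passages on the Day 7 (+2) visit window and on the fixed second-course dosing days must be reconciled, so that it is clear what was intended after a Day 8 or Day 9 visit.
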